The data that will be shared with the Medical University of South Carolina (MUSC) will be de-identified, age, race and ethnicity will be reported as required by NIH (see attached template that will be requested for reporting purposes) as part of a final report to MUSC.

X.7

Does your study meet the NIH criteria for a Certificate of Confidentiality or will you be applying for Certificate of Confidentiality?

No

XI. Data Analysis

XI.1

Describe the analysis methods you will use, including, if applicable, the variables you will analyze

The generalized estimating equation (GEE) framework will be utilized to assess changes over time in fatigue and quality of life measures. An interaction term between time and treatment will allow us to test the within- and between-treatment differences over all time points. Using histograms, variable distributions will be assessed to decide which link function to specify when modeling each outcome. To account for the inherent correlation that occurs in repeated measures data, we will cluster on subject ID. In addition to

examining the unadjusted relationship between the time-treatment interaction and each outcome, we will consider the addition of control variables, which will reduce the likelihood of unaccounted confounders. The control variables being considered for inclusion in the adjusted models are age, sex, and disease duration. For each outcome, models will be fit for all possible combinations of control variables. The predictor set that yields the smallest Akaike information criterion (AIC) will be considered the optimal control variable set to adjust associations between the main predictor and the outcomes. Statistical significance will be assessed at the $\alpha = 0.05$ level.

XI.2

Provide the rationale or power analysis to support the number of subjects proposed to complete this study.

The sample size calculation was based on the Fatigue Severity Scale data from our own preliminary data that assessed the effects of multiple sessions of 4 mA tDCS on fatigue in people with multiple sclerosis. The effect size of this difference = 0.91 (Cohen's d). With alpha fixed at 0.05, we would need 20 total subjects in each group (tDCS and SHAM; details below) to achieve 80% power in a two-tailed independent samples test. Therefore, to account for 20% data and subject attrition, we will recruit 25 subjects per group (150 total).

XII. Future Research

XII.1

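### The covariate rule in XI.1 relies on an AIC that GEE does not have, no result is named as decisive, and several fatigue and QOL measures are tested at 0.05 without a primary, although only one FSS comparison was sized

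*Combined protocol and SAP*

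**What the plan says.** **Model.** XI.1 uses GEE clustered on subject for the fatigue and QOL measures. On the treatment effect it states: "An interaction term between time and treatment will allow us to test the within- and between-treatment differences over all time points". The link is left to the data: "Using histograms, variable distributions will be assessed to decide which link function to specify when modeling each outcome".

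**Covariates.** XI.1 plans an unadjusted analysis of each outcome and, alongside it, adjusted models. The candidates are three: "The control variables being considered for inclusion in the adjusted models are age, sex, and disease duration". The search is exhaustive and is run separately by outcome: "For each outcome, models will be fit for all possible combinations of control variables". AIC then settles the choice: "The predictor set that yields the smallest Akaike information criterion (AIC) will be considered the optimal control variable set".

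**Testing.** "Statistical significance will be assessed at the" 0.05 level, without saying whether this applies per test or overall. No primary outcome, primary visit or testing order is named.

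**Sizing.** In XI.2, "The sample size calculation was based on the Fatigue Severity Scale data" with d = 0.91, giving 20 per group to "achieve 80% power in a two-tailed independent samples test", and 25 recruited per group after 20% attrition. XI.2 does not call the FSS primary.

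**Measures and visits.** VII.E.4 lists the Fatigue Assessment Scale (FAS), the FSS and the EQ-5D-5L. The objective in I.5 adds performance fatigability, for which VII.E.6 describes an isokinetic test. Hypotheses 1 and 2 in I.5 cover the end of treatment, 3 weeks and 6 weeks, but name no measure and set no hierarchy.

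**The concern.** There are two problems of unequal weight.

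1. **A rule that cannot be carried out.** AIC needs a maximised likelihood, and GEE solves estimating equations without specifying one. An analyst must either improvise or accept a software figure based on an independence likelihood that ignores the within-subject correlation. Because XI.1 does not rank the unadjusted and adjusted analyses, two results per outcome are available with nothing to say which counts.

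2. **No designated primary.** With several measures, three post-baseline visits and no order, a significant result on any one of them could be presented as the trial's result. The 80% power claim covers only one between-arm FSS test. This second problem carries the severity.

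**Working it through.** **1. The plan's own figure.** Inputs from XI.2: d = 0.91, two-sided alpha 0.05, power 80%, attrition 20%. The exact two-sample t-test needs 19.96, so 20 per group, and has 80.1% power at 20. Then 20 / 0.80 = 25, and 25 × 6 = 150. The figure reproduces, for one FSS comparison at the full 0.05.

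**2. What the AIC search does.**
- Three candidate covariates give 2³ = 8 models per outcome.
- Suppose a subject-level covariate has no effect and the independence-likelihood AIC is used over 4 visits. The likelihood-ratio statistic is inflated by 1 + 3 × ICC, so the covariate is kept with probability P(χ²₁ > 2 / (1 + 3 × ICC)). With ICC 0.5 this is P(χ²₁ > 0.80) = 37%; with ICC 0.7 it is P(χ²₁ > 0.645) = 42%. Under a correct likelihood it is P(χ²₁ > 2) = 16%. The ICCs are assumed. These are retention rates, not error rates.
- Effect on the time-by-treatment test (6,000 simulated null trials, ICC 0.6 assumed, identity link): rejection 0.0605 unadjusted and 0.0605 after AIC selection with complete data; 0.0575 and 0.0567 with 20% dropout.
- The reason is algebraic. With an identity link and complete data, a covariate that is constant over visits shifts all of a subject's fitted values equally. It cancels from within-subject contrasts, so age, sex and disease duration leave the interaction estimate unchanged.

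**3. Chance of at least one false positive.** The documents give neither the number of tests nor their correlations, so correlations of 0.3 to 0.7 are assumed. The quantity is 1 − P(no test rejects) for correlated normal statistics, each at two-sided 0.05 (400,000 draws for the two-, three-, six- and nine-test cases). A joint test has 3 degrees of freedom (three post-baseline visits).

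| Reading of XI.1 | Tests | Correlation 0.7 to 0.3 |
|---|---|---|
| One joint test each: FSS, FAS | 2 | 8–10% |
| Adding EQ-5D-5L | 3 | 11–14% |
| Adding performance fatigability | 4 | 13–18% |
| Separate visits, 2 outcomes × 3 | 6 | 16–24% |
| Separate visits, 3 outcomes × 3 | 9 | 20–33% |

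Every reading exceeds 5%. A single FSS primary test keeps 5%.

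**4. What the Day 1 value offers.** Let ρ be the correlation between Day 1 and follow-up. The change score has variance 2(1 − ρ)σ² and the Day 1-adjusted comparison (1 − ρ²)σ², a ratio of (1 + ρ)/2: 0.75 at ρ = 0.5 and 0.85 at ρ = 0.7. Simulated power at 20 per arm, with three further null covariates in the model, is 86.4% (ρ = 0.5) and 82.0% (ρ = 0.7), against 79.9% and 80.1% for change scores, if d = 0.91 is on the change scale. If it is on the post-score scale, the figures are 86–96% against 80–95%. Simulated type I error was 0.051 and 0.049.

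**The case against.** **AIC governs only the additional adjusted models; an unadjusted analysis is already planned.** This stands, and it limits the point. A reader might infer that the covariate search inflates the type I error. The simulation and the algebra do not support that. What remains is a rule that cannot be executed and no statement of which analysis decides. Substituting QICu, or AIC under a maximum-likelihood mixed model, would make the search executable but would not make it useful for this test.

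**The Day 1 covariate is a matter of efficiency.** This also stands. XI.1 models change over time with baseline in the response, which is legitimate. The gain is modest and depends on an assumed correlation. Likewise, choosing the link from histograms is a loose specification rather than an error in itself.

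**A hierarchy may exist elsewhere.** VII.B.11 says there is no separate written protocol, but it does not count a grant application as one, and VII.A.10 mentions a pilot grant. Only absence from the supplied documents is shown.

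**The sample size might be read as wrong.** It is not; the arithmetic reproduces. The sized comparison is simply not designated as the decisive one.

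**EQ-5D-5L might be read as not collected on Day 1.** It is missing from the Day 1 list in VII.E.6, but that list is introduced as the vascular study and is visibly incomplete: the same section then refers to a prior PET scan, MRI, strength testing and fatigue testing, none of which is on it. The omission is a question to settle, not proof.

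**Conclusion.** The point holds and should be fixed before analysis. Two facts rest on the documents alone: the adjusted-model rule is undefined under GEE with no decisive analysis named, and no primary outcome, visit or order is given although one FSS comparison was sized. The size of the multiplicity problem, 8–18% with joint tests and 16–33% with separate visit tests, depends on the assumed correlations and on how many measures and visits are counted. The AIC rule must go because it cannot be followed and gains nothing for the time-by-treatment test, not because it produces false positives.

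**What to change.** **(a) One decisive model.** Delete the AIC and histogram rules. For continuous outcomes, pre-specify an identity-link model on the post-baseline visits with visit, treatment, visit-by-treatment, the outcome's Day 1 value, age and sex. Include disease duration only if the analysis population is limited to post-COVID subjects: the never-COVID controls that VI.13 and VII.E.2 randomise have no value for it. Fit it by REML with Kenward-Roger, or by GEE with a small-sample-corrected standard error.

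**(b) One primary test.** Name the between-arm FSS difference at the first post-treatment assessment as the single primary test at two-sided 0.05. Label all other measures and visits secondary or exploratory. Whether to add a fixed order or a Holm adjustment among the secondaries is the sponsor's choice.

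**(c) Reconcile before fixing the primary visit and population.**
- Session count: Hypothesis 1 in I.5 refers to five sessions. VII.E.6 gives a first session on Day 1 and treatment on the next four days, but no stimulation on Day 5. VII.E.19 pays for four sessions (4 × $15 = $60).
- Who is randomised and followed: VI.13 and VII.E.2 randomise all three populations, while VII.E.6 ends asymptomatic participation after one session.
- Whether EQ-5D-5L is collected on Day 1 (VII.E.4 against VII.E.6).

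**Cost.** No added subjects or visits, and Day 1 FSS is already collected. The sized unadjusted comparison has 80.1% power at 20 per group; Day 1 adjustment raises this to about 82–86% if d = 0.91 is on the change scale and the baseline correlation is 0.7 to 0.5. The price is that fewer results can be called significant. The reconciliations reach beyond the wording of XI.1.

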- *Participants will be told that the research includes completion of a particular task, when in fact, that task will not be administered.*
- *Study is designed to introduce a new procedure (or task) that participants are not initially told about.*
- *If yes, a waiver of informed consent must be requested under question IV.3.*

• No

VII.E. Project Description (E)

VII.E.1

Will subjects be randomized?

Yes

VII.E.1.a

Will any subjects be blinded to which study arm they have been assigned?

Yes

VII.E.1.b

Does the protocol permit telling subjects their treatment assignment at the end of the entire study?

Yes

VII.E.1.c

Describe the circumstances under which subjects will be told what study arm they have been assigned.

At the end of all sessions, and upon request by the subject, the participant will be informed about the stimulation condition they experienced.

VII.E.2

Describe randomization scheme/assignment including ratio such as 1:1, 2:1 etc.

The study will be a double-blind, sham-controlled, randomized parallel design. Post-COVID-19 patients with fatigue, post-COVID-19 patients without fatigue, and subjects without a history of a COVID-19 diagnosis (controls) will be randomly assigned to one of two groups. One group will

receive tDCS (tDCS Group; n = 25 in each group of subjects; 75 total) and the other group will receive SHAM (SHAM Group; n = 25 in each group of subjects; 75 total). The study will involve nine sessions at the INPL.

VII.E.3

Will any questionnaires, surveys, or written assessments be used to obtain data directly from subjects in this study?

Yes

VII.E.4

List all questionnaires, surveys, written assessments and ATTACH each one to the application.

(NOTE: You are NOT prohibited from attaching copyrighted materials to this application)

Chalder Fatigue Scale

C19-YRS-Covid-Rehab-screening-tool

Fatigue Assessment Scale (FAS)

Fatigue Severity Scale (FSS)

EQ-5D-5L Quality of Life questionnaire

Visual analog scale for pain

COVID19 Severity Survey

Pittsburgh Sleep Quality Index (PSQI) (to determine sleep quality)

International Physical Activity Questionnaire (IPAQ) (to quantify recent physical activity levels)

VII.E.5

Does this project involve creating any audiotapes, videotapes, or photographs?

No

VII.E.6

Provide a detailed description in sequential order of the study procedures following the consent process - DO NOT cut and paste from the Consent Document.

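### The planned GEE states no weights, imputation or working correlation for the expected 20% attrition, so fatigue-related dropout could bias the week-3 and week-6 effects

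*Combined protocol and SAP*

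**What the plan says.** Section XI.1 of the combined protocol and SAP sets the method: "The generalized estimating equation (GEE) framework will be utilized to assess changes over time in fatigue and quality of life measures". The effect of interest is a time-by-treatment term: "An interaction term between time and treatment will allow us to test the within- and between-treatment differences over all time points". On correlation within subjects it says only "To account for the inherent correlation that occurs in repeated measures data, we will cluster on subject ID". The link function is to be chosen for each outcome from histograms, and the candidate covariates are age, sex and disease duration. No weights, imputation, missing-data assumption, working correlation, analysis population or sensitivity analysis is stated. VII.B.11 says that no separate protocol accompanies the form, so these details are not deferred to one.

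Section XI.2 bases the sample size on a comparison at a single time point and then inflates it: "Therefore, to account for 20% data and subject attrition, we will recruit 25 subjects per group (150 total".

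Under VII.E.6, symptomatic subjects are tested on Day 1, on Day 5, and three and six weeks after Day 5. Hypothesis 2 in I.5 concerns the last two visits. VII.E.7 says that no attempt will be made to reach participants who are lost.

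**The concern.** Raising the number from 20 to 25 per group replaces lost information. It does nothing about who is lost.

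A GEE without weights or imputation is generally consistent only when missingness is unrelated to the outcomes, observed or not (missing completely at random, MCAR). In a fatigue trial it is plausible that subjects who are still very tired on Day 5 are less likely to come back for two further laboratory visits. If tDCS works, there are more such subjects under sham. The sham subjects who return would then look better than the sham arm as a whole, and the treatment difference at weeks 3 and 6 would be distorted.

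The data needed to correct for this, the Day 1 and Day 5 scores, are already scheduled. A likelihood-based repeated-measures model uses them directly and is valid under the weaker missing-at-random (MAR) condition, in which dropout may depend on observed scores. At stake is the estimate for Hypothesis 2, and whether it depends on a working correlation that could be chosen after the data are seen.

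**Working it through.** **1. The plan's own figures (XI.2).** Inputs: "The effect size of this difference = 0.91 (Cohen's d"), "With alpha fixed at 0.05, we would need 20 total subjects in each group", and "to achieve 80% power in a two-tailed independent samples test".

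- Normal approximation: n = 2(1.960 + 0.842)² / 0.91² = 2 × 7.85 / 0.828 = 18.96, so 19 per group.
- Exact t-test: 19.96, so 20 per group (power 80.1% at n = 20). This matches the plan.
- Inflation: 20 / (1 - 0.20) = 25 per group; 25 × 6 groups = 150. This also matches.

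The arithmetic is right, so the point does not concern the sample size.

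**2. How the bias arises.** With a saturated visit-by-arm model and independence working correlation, the week-6 estimate is the difference in means among those still observed. If dropout depends on the Day 5 score, and scores are jointly normal with unit SD, each arm's week-6 mean shifts by ρ × s. Here ρ is the Day 5 to week 6 correlation and s is the shift in mean Day 5 score among those who stay. The bias is therefore ρ × (s_tDCS - s_sham). If the true effect is zero and the dropout rule is the same in both arms, the two shifts are equal and the bias is zero. If tDCS works, more sham subjects drop out, s_sham is the more negative, and the estimated effect shrinks.

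**3. Size under stated assumptions.** None of the following is in the documents, except the 20% and the 0.91:

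- true effect -0.91 SD at every visit after treatment;
- 20% dropout overall, all of it after Day 5;
- dropout depends on the observed Day 5 score, with the same rule in both arms and log-odds of 0.5 to 2 per SD (odds ratio about 1.6 to 7.4);
- within-subject correlation 0.6 compound symmetric, or 0.8 autoregressive.

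Large-sample simulation (200,000 per arm), week-6 effect:

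| Estimator | Estimate (truth -0.91) | Departure |
|---|---|---|
| GEE, independence | -0.89 to -0.78 | about 2% to 15% too small |
| GEE, exchangeable | -0.90 to -0.93 | within about 2% |
| Likelihood model, correct covariance | about -0.91 | negligible |
| Any of these, MCAR dropout | about -0.91 | none |
| Any of these, true effect zero | about 0.00 | none |

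From the rounded ends of the first row, (0.91 - 0.89)/0.91 = 2% and (0.91 - 0.78)/0.91 = 14%. At log-odds of 0.5 to 0.7 the independence GEE gives -0.89 to -0.87. At 1 to 2 it gives about -0.85 to -0.78, with dropout of 26-29% under sham against 11-14% under tDCS.

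**4. Other correlations.** With correlation 0.5 or 0.7 (exchangeable or autoregressive), odds ratio 2 or 3 per SD and the same rule in both arms, independence GEE gave -0.89 to -0.83. Exchangeable GEE, with its correlation fixed at that value rather than estimated, gave -0.90 to -0.94. The correct working correlation gave -0.90 to -0.91.

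**5. Against the trial's precision.** With 20 completers per arm, the standard error of a simple difference is √(1/20 + 1/20) = 0.32 SD. A bias of 0.02 to 0.13 SD is therefore 0.02/0.32 = 0.06 to 0.13/0.32 = 0.41 standard errors.

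**The case against.** The strongest reply is that the defect is read out of silence. XI.1 does not say that the GEE is unweighted or that it uses independence working correlation. It clusters on subject precisely to respect the repeated measures. With an identity link, roughly normal scores and a well-chosen working correlation, a GEE comes close to validity under MAR, and the exchangeable results above show little bias. This stands in part: it limits the size of the problem. It does not remove it, because the plan commits to no working correlation and leaves the link open, so nothing in it secures the favourable case.

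Three stronger readings are tempting, and the documents support none of them.

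- A reader might infer a false-positive risk. Simulations in which dropout depends on fatigue in opposite directions in the two arms give an effect about 23% too small, or a spurious difference of about 0.21 SD when there is no true effect. VII.E.2 describes a double-blind, sham-controlled design, and nothing in the text suggests dropout of that kind. Under the same rule in both arms, a null effect stays null.
- A reader might infer that the whole 20% falls at weeks 3 and 6. XI.2 speaks of data and subject losses in general and does not place them. Separate follow-up visits make later loss plausible, but some may occur before Day 5. Those subjects would have no Day 5 score for any method to use.
- A reader might infer that dropout will be related to fatigue. The documents do not say so; it is a reasonable possibility to plan for.

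It is also fair to say that the bias is modest beside the sampling error of so small a trial, and that a Gaussian model gives up the freedom in XI.1 to suit the link to each outcome. The fix below allows for the second point.

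**Conclusion.** The concern holds in a limited form. The plan expects 20% losses, does not seek to recover lost participants, and names a method that, as stated, is generally valid only under MCAR. The week-3 and week-6 effects can therefore be biased if dropout depends on earlier fatigue. Under the assumptions listed in the working, the week-6 bias runs from negligible (exchangeable working correlation) to about 15% attenuation (independence with strongly score-dependent dropout), and it is zero if there is no treatment effect. These sizes rest on assumed timing, mechanism and correlations; the direction is towards a smaller effect only for the independence GEE in the same-rule scenario. The change is worth making before analysis because the size of the error turns on a choice that the plan leaves open, and because a MAR-valid analysis can use scores already being collected. It does not call the sample size or the design into question.

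**What to change.** In XI.1:

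- For fatigue and quality-of-life scores that are approximately continuous, make a likelihood-based repeated-measures model the analysis. Treat visit as a category, include the visit-by-treatment interaction, use an unstructured covariance, and include all observed visits of all randomised symptomatic subjects. State that it assumes MAR.
- Where an outcome needs a non-identity link and GEE is kept, use inverse-probability weights or multiple imputation based on Day 1 and Day 5 scores, and name the working correlation in advance.
- Optionally, add a delta-adjusted sensitivity analysis at week 6, since neither approach covers dropout that depends on unobserved scores.

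The cost is revised wording and slightly more analysis work, with no new data, visits or subjects. The likelihood model brings its own reliance on approximate normality and on the covariance structure. With four visits, an unstructured covariance has 4 × 5 / 2 = 10 parameters, to be estimated from at most 50 symptomatic subjects.
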